**4.1 Study Population**

All inclusion and exclusion criteria must be evaluated for eligibility.

**4.1.1 Inclusion Criteria**

*A volunteer must meet all of the following criteria:*

1. Able and willing to complete the informed consent process.
2. Available for clinical follow-up through the last study visit.
3. 18 to 60 years of age.
4. In good general health without clinically significant medical history.
5. Willing to have blood samples collected, stored indefinitely, and used for research purposes.
6. Able to provide proof of identity to the satisfaction of the study clinician completing the enrollment process.
7. Physical examination without clinically significant findings within the 84 days prior to enrollment.
8. Have screening laboratory values within 84 days prior to enrollment that meet the following criteria:
  - WBC 2,500-12,000/mm^3

- WBC differential either within institutional normal range or accompanied by the Principal Investigator (PI) or designee approval
- Platelets = 125,000 – 400,000/mm^3
- Hemoglobin within institutional normal range or accompanied by the PI or designee approval
- Creatinine  $\leq 1.1$  x upper limit of normal (ULN)
- ALT  $\leq 1.25$  x ULN
- Negative for human immunodeficiency virus (HIV) infection by a Food and Drug Administration (FDA) approved method of detection
- Negative for Hepatitis B core antibody (HBcAb) and Hepatitis C virus antibody (HCV Ab)

***Criteria applicable to women of childbearing potential:***

9. If a woman is of reproductive potential and sexually active with a male partner, then she agrees to use an effective means of birth control from the time of study enrollment until the last study visit, or to be monogamous with a partner who has had a vasectomy.
10. Negative human chorionic gonadotropin ( $\beta$ -HCG) pregnancy test (urine or serum) on day of enrollment and product administration.

**4.1.2 Exclusion Criteria**

***A volunteer will be excluded from study participation if one or more of the following conditions apply:***

1. Previous receipt of a licensed or investigational monoclonal antibody or Ebola vaccine.
2. Weight >100 kg.
3. Any history of a severe allergic reaction with generalized urticaria, angioedema or anaphylaxis prior to enrollment that has a reasonable risk of recurrence during the study.
4. Hypertension that is not well controlled.
5. Woman who is breast-feeding or planning to become pregnant during study participation.
6. Receipt of any investigational study product within 28 days prior to enrollment.
7. Any other chronic or clinically significant medical condition that in the opinion of the investigator would jeopardize the safety or rights of the volunteer, including but not limited to: diabetes mellitus type I, chronic hepatitis; OR clinically significant forms of: drug or alcohol abuse, asthma, autoimmune disease, psychiatric disorders, heart disease, or cancer.
8. Bleeding disorder diagnosed by a doctor (e.g. factor deficiency, coagulopathy, or platelet disorder requiring special precautions) or significant bruising or bleeding difficulties with IM injections or blood draws.
9. Use of angiotensin-converting enzyme (ACE) inhibitors or other potential nephrotoxins.

## 4.2 Clinical Procedures and Laboratory Assays

Safety evaluations will include laboratory studies, medical history, and physical assessment by clinicians. The study schedule is provided in Appendix III. Total blood volume drawn from each subject will comply with the NIH CC Guidelines available on the NIH intranet at the following link: <http://cc-internal.cc.nih.gov/policies/PDF/M95-9.pdf>.

### 4.2.1 Screening

Screening for this study will be completed through the VRC's screening protocol, VRC 500 (NIH 11-I-0164); no screening evaluations will be performed within this protocol. Volunteers will be recruited through Institutional Review Board (IRB)-approved advertising.

The evaluations and sample collection that will be included in screening are a medical history, physical exam, any laboratory tests needed to confirm eligibility, and pregnancy test for females of reproductive potential. The screening evaluations are outlined in Appendix III. Additional assessments of health may be conducted at screening based on clinical judgment. Only subjects determined to be eligible after screening is completed will be enrolled. Research samples of peripheral blood mononuclear cells (PBMCs), plasma and serum will also be collected. VRC 608 informed consent documents will be reviewed. Counseling related to potential risks of the study product and pregnancy prevention will be performed. An Assessment of Understanding (AoU) will be completed in association with enrollment into VRC 608. Records will be maintained that document the reason(s) why a screened individual was not enrolled.

### 4.2.2 Enrollment, Study Days and Visit Numbers

Clinicians must discuss the target dates and timing of the study product administration and sample collections before completing each enrollment to help ensure that the subjects can comply with the projected schedule. In this study, enrollment is defined as the assignment of a study identification number and study group schedule in the clinical database. Informed consent must be obtained prior to enrollment. Enrollment may occur on the same day as product administration at Visit 02 (Day 0) or in advance of product administration at Visit 01R (Day -28 to Day 0).

Visit 02 (Day 0) is defined as the day of MAb114 administration. Day 0 is preferably conducted within 14 days after enrollment but may occur up to 28 days after enrollment if needed. This period may be increased with PI approval.

For calculating elapsed days following Day 0, each subsequent calendar date is labeled by the next sequential "Study Day" as shown in the Schedule of Evaluations, Appendix III. Since there may be more than one research sampling timepoint of interest per study day, each sample collection timepoint has its own "Visit Number." For this reason, there may be more than one visit number recorded on the same calendar date.

Medical history and Day 0 evaluations prior to the study product administration are the baseline for subsequent safety assessments.

### 4.2.3 Administration of MAb114

All study product administrations will be completed according to the group assignment. For women of childbearing potential, study product administration may not proceed unless a negative pregnancy test has been obtained. Prior to study product administration, temperature, blood

pressure, heart rate (pulse) and weight will be collected, and a targeted physical examination will be conducted.

In all study groups, the subject will be observed for at least 4 hours following completion of product administration. Following the first product administration for each group, the study team will wait at least 3 days before administering MAb114 to additional subjects within that group.

On Day 0, an IV access will be established in an arm vein using aseptic technique. A different site may be used for collection of PK blood samples; however, the same site may be used after flushing the line if another site is not available. MAb114 will be diluted with normal saline and infused over a period of approximately 30 minutes; longer infusion times will be permitted. Infusion should continue until the bag is empty. If the subject experiences side effects during the infusion, the rate of infusion may be slowed or stopped to alleviate the symptoms.

Procedures for MAb114 preparation and administration are described in Section 7.

#### **4.2.4 Solicited Adverse Events and Clinical Follow-up**

Subjects will be asked to record temperature and systemic symptoms daily for 3 days after the study product administration. Subjects will be trained and encouraged to use the electronic database to record reactogenicity but will have the option to use a paper diary card. When the 3-day diary parameters are recorded directly by the subject into the database, the subject's electronic record will be available to clinicians in real time and will be the source for these data. If concerns arise based on the subject's report of symptoms, clinicians may follow up with additional phone calls during the reactogenicity period as needed. The paper diary will be the source document, if used by the subject. When neither a paper nor electronic diary is available from the subject, the clinician will note the source of reactogenicity information recorded in the study database.

For this study, solicited systemic parameters occurring during the 3 days after receipt of study product will include: unusually tired/feeling unwell, muscles aches, headache, chills, nausea and joint pain. Subjects will also record highest measured temperature daily. Subject diaries are reviewed for accuracy and completeness at follow-up visits and reactogenicity is recorded without an attribution assessment. Clinicians will follow and collect resolution information for any reactogenicity symptoms that are not resolved within 3 days.

Local symptoms will be assessed and recorded by the clinicians. Local reactogenicity parameters will include pain/tenderness, swelling, redness, bruising, and pruritus (itchiness) at the product administration site. Clinicians will assess the study product administration site(s) for local reactogenicity on the day of product administration after completion of the administration and during the scheduled follow-up time points as noted in the Schedule of Evaluations (Appendix III).

Events that may require a clinic visit include rash, urticaria, fever of 38.6°C (Grade 2) or higher lasting greater than 24 hours or significant impairment in the activities of daily living (such as those consistent with Grade 2 or higher impairment). Additionally, arthralgia or other clinical concerns may prompt a study visit based on the judgment of a study clinician.

Clinical laboratory assays and clinical evaluations will assess for safety and tolerability at specified intervals post study product administration. Any new or concerning symptoms will be fully assessed to include specialty consultation at the NIH CC as clinically indicated.

#### 4.2.5 Pharmacokinetics

PK samples will be collected as close as reasonably possible to the target timepoints. Because the time of blood collection is critical for PK analysis, the actual time of the phlebotomy will be recorded for all samples. The PK target timepoints are defined in the Schedule of Evaluations (Appendix III).

#### 4.2.6 Schedule of Evaluations

The Schedule of Evaluations (Appendix III) provides details on the study schedule and the permitted visit windows. After enrollment, deviations from the visit windows are discouraged but will be permitted at the discretion of the PI or designee and will be recorded as protocol deviations.

Additional visits and blood draws may be scheduled during the study if needed to assess subject safety or for sample collection in support of immunological testing provided the cumulative blood collection volume complies with NIH CC guidelines. After study completion, subjects may be invited to participate in one of the VRC sample collection protocols (VRC 200 or VRC 900) for follow-up sample collection.

Any evaluation for an adverse event (AE) or possible exacerbation of a pre-existing condition may be scheduled at the study team's discretion as a "protocol-related" evaluation.

#### 4.2.7 Concomitant Medications

Only routine prescription and over the counter medications, and herbal supplements, will be entered in the database at the time of enrollment. Subsequently, concomitant medications associated with an AE that requires expedited reporting or the development of a new chronic condition requiring ongoing medical management will be recorded in the database. Otherwise, concomitant medications taken throughout the study will be recorded in the subject's chart as needed for general medical documentation but will not be recorded in the study database.

### 4.3 Criteria for Dose Escalation

There are two dose escalation reviews in this study. The PSRT (Section 8.8) will conduct an interim safety data review before the dose escalation may occur. The PSRT must assess the data as showing no significant safety concerns before proceeding with enrollment of each subsequent group.

- The first dose escalation review (from 5 mg/kg IV to 25 mg/kg IV) will occur when all 3 subjects who received the 5 mg/kg IV dose have completed Visit 05, the Day 7 safety follow-up visit. The PSRT review will determine whether enrollment into Group 2 may begin.
- The second dose escalation review (from 25 mg/kg IV to 50 mg/kg IV) will occur when all 5 subjects who received the 25 mg/kg IV dose have completed Visit 05, the Day 7 safety follow-up visit. The PSRT review will determine whether enrollment into Group 3 may begin.

If there are discontinuations from the study before there are sufficient data to conduct the dose continuation review for a specific group, then extra subjects may be enrolled into that group to obtain the requisite data on at least 3 (Group 1) or 5 (Group 2) subjects. Additionally, AEs assessed as related to study product at the time of a dose escalation review may warrant enrollment of additional subjects into a dose group to reassess safety before proceeding to a higher dose.

Consultation with the IRB and FDA, if needed, as per study pause criteria (Section 4.5) will occur if indicated by the review. The IRB will be provided with documentation of the safety review process and notification of the dose escalation.

#### 4.4 Criteria for Discontinuing Study Participation

A subject may be discontinued from study participation for the following reasons:

1. Subject decides to discontinue participation;
2. Subject develops a medical condition that is a contraindication to continuing study participation;
3. The IND sponsor or regulatory authority stops the study;
4. The PI (or designee) assesses that it is not in the best interest of the subject to continue participation in the study or that the subject's compliance with the study is not sufficient.

#### 4.5 Criteria for Pausing the Study and Resuming the Study

Administration of the study product and new enrollments will be paused by the PI according to the criteria noted below. In the event of a pause, the IND Sponsor Medical Officer (MO) and the PSRT will be promptly notified. Pause criteria are as follows:

- **One** (or more) subject experiences a **Serious Adverse Event** (SAE) that is assessed as related to study product, or
- **Two** (or more) subjects experience the same **Grade 3 or higher AEs** assessed as related to study product (other than self-limited Grade 3 solicited reactogenicity AEs).

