**6.4.3 Safety Analysis**

Summaries of the number and percentage of subjects experiencing any AE or reactogenicity will be tallied by group and presented along with exact 95% confidence intervals for the proportion.

Solicited Adverse Events:

Solicited AE data is collected after each dose administered in this study. The number and percentage of subjects experiencing each type of solicited sign or symptom will be tabulated by severity. For a given sign or symptom, each subject’s solicited AEs will be counted once under the maximum severity for all assessments.

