### Adverse Events:

Unsolicited AEs are coded into Medical Dictionary for Regulatory Activities (MedDRA) preferred terms. The number and percentages of subjects experiencing each specific AE will be tabulated by severity and relationship to treatment. For the calculations in these tables, each subject's adverse experience will be counted once under the maximum severity or strongest recorded causal relationship to treatment.

A complete listing of adverse experiences for each subject will provide details including severity, relationship to treatment type, onset, duration and outcome.

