## 8.2 Risks and Benefits

### 8.2.1 Risks

MAb114: There is no prior human experience with administration of MAb114.

MAbs: Administration of MAbs may cause immune reactions such as acute anaphylaxis, serum sickness and the generation of antibodies. However, these reactions are rare and more often associated with MAbs targeted to human proteins or with the use of murine MAbs that would have

a risk of human anti-mouse antibodies [24]. In this regard, because MAb114 is targeted to a viral antigen and is a human MAb, it is expected to have a low risk of such side effects.

Typically, the side effects of MAbs are mild to moderate and may include fever, chills, rigors, nausea, vomiting, pain, headache, dizziness, shortness of breath, bronchospasm, hypotension, hypertension, pruritus, rash, urticaria, angioedema, diarrhea, tachycardia or chest pain. Clinical use of MAbs that are targeted to cytokines or antigens associated with human cells may be associated with an increased risk of infections [24]; however, this is not expected to be a risk for a MAb targeted to a viral antigen.

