## Appendix IV: Assessment of Relationship to Study Product and Adverse Event Severity Grading

### Assessment of Causality Relationship of an Adverse Event to Study Product:

The relationship between an adverse event (AE) and the product will be assessed by the investigator on the basis of his or her clinical judgment and the definitions below.

- **Definitely Related.** The AE and administration of study product are related in time, and a direct association can be demonstrated.
- **Probably Related.** The AE and administration of study product are reasonably related in time, and the AE is more likely explained by study product than other causes.
- **Possibly Related.** The AE and administration of study product are reasonably related in time, but the AE can be explained equally well by causes other than study product.
- **Not Related.** There is not a reasonable possibility that the AE is related to the study product.

For purposes of preparing data reports in which AE attributions are limited to “**Related**” or “**Not Related**”, in this protocol, the “**Definitely, Probably and Possibly**” attributions will be mapped to the “**Related**” category. The definitions that apply when these two categories alone are used are as follows:

- **Related** – There is a reasonable possibility that the AE may be related to the study product.
- **Not Related** – There is not a reasonable possibility that the AE is related to the study product.

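### The Grade 3+ pause rule in 4.5 needs a relatedness judgement that 4.2.4 says is not made for diary reactions, in conflict with Appendix IV

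*Combined protocol and SAP*

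**What the plan says.** Section 4.5 has two pause criteria. The first is one related SAE. The second is the same Grade 3 or higher AE in at least two subjects, "assessed as related to study product (other than self-limited Grade 3 solicited reactogenicity AEs". The exclusion covers only the self-limited Grade 3 part of the solicited reactions. A Grade 4 solicited reaction, or a Grade 3 one that is not self-limited, still counts once it is judged related. The protocol does not define self-limited.

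Section 4.2.4 describes how solicited data are collected. Systemic symptoms and temperature go into a 3-day subject diary, and on review "reactogenicity is recorded without an attribution assessment". The sentence has no exception for grade or duration. For symptoms still present after 3 days, the section asks clinicians for follow-up and resolution data, not for causality. Local reactions have a separate paragraph, "Local symptoms will be assessed and recorded by the clinicians", which does not mention attribution.

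Section 6.4.3 follows the same split. For solicited events, "each type of solicited sign or symptom will be tabulated by severity". For unsolicited events, "each specific AE will be tabulated by severity and relationship to treatment".

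Appendix IV states a general rule: the relationship between an AE and the product "will be assessed by the investigator on the basis of his or her clinical judgment". It neither mentions solicited reactions nor refers to the exemption in 4.2.4.

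**The concern.** The exclusion in 4.5 makes sense only if other solicited reactions can trigger the rule, so the authors evidently meant severe or persistent ones to count. They count only with a related judgement, and the collection procedure for systemic reactions says none is made. Staff who follow 4.2.4 to the letter would never produce the input that the rule needs.

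This matters because the second criterion is the only pre-set pause rule for non-serious Grade 3 or higher events in a first-in-human study. The affected symptoms are also plausible product effects. Section 8.2.1 says that side effects of monoclonal antibodies "may include fever, chills, rigors, nausea, vomiting, pain, headache", and fever, chills, nausea and headache are all diary items. Other effects on that list, such as urticaria, bronchospasm and hypotension, are not diary items. They are attributed as unsolicited AEs and are not affected.

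**Working it through.** **Step 1. Which events are affected.**

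| Event | Attribution under the text | Route to a pause |
|---|---|---|
| Unsolicited AE, Grade 3+ | Appendix IV; tabulated by relationship (6.4.3) | Second criterion works |
| Any reaction that is an SAE | Appendix IV; relatedness also needed for IRB reporting (5.4.4) | First criterion, one subject if related |
| Local solicited reaction, Grade 4 or non-self-limited Grade 3 | 4.2.4 silent; Appendix IV applies unopposed | Second criterion works |
| Systemic diary reaction, self-limited Grade 3 | None under 4.2.4 | Excluded by 4.5 |
| Systemic diary reaction, non-serious, Grade 4 or non-self-limited Grade 3 | 4.2.4 says none; Appendix IV says assess | **Conflict** |

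Only the last row is in question.

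**Step 2. The plan's own figures.** Table 4 gives the probability of more than one event, which matches a two-subject trigger. With n subjects and probability q per subject that a counted event occurs,

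P(X ≥ 2) = 1 − (1 − q)^n − n·q·(1 − q)^(n−1).

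For n = 5 and q = 0.1: 1 − 0.5905 − 0.3281 = 0.081, as in Table 4. All 15 cells of this type in Table 4 (n = 3, 5 and 10) reproduce to rounding.

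**Step 3. Exposure left at the data cut.** Section 1.6.1 reports 13 subjects dosed by 24 July 2018 (3, 5 and 5 in the three groups). All 13 completed diary cards, and no solicited reaction exceeded mild. Both events needed for the trigger would therefore have to come from subjects not yet dosed:

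- minimum enrolment: 18 − 13 = 5, all at 50 mg/kg, since Group 3 has 10 planned and 5 dosed;
- cap: 30 − 13 = 17.

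Section 1.6.1 prints the systemic result as 3 of 11 with 23.1%. Since 3/13 = 23.1% and 3/11 = 27.3%, the denominator 13 is used here. The exact two-sided 95% upper bound for 0/13 is 1 − 0.025^(1/13) = 0.247. It applies to any solicited reaction above mild, a far broader class than the one at issue.

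**Step 4. Effect of missing attribution.** Put q = r × s. Here r is the true rate of one specific qualifying reaction, assumed to be product-related and independent between subjects, and s is the share of cases attributed as related. Neither r nor s is given in the documents. The values 0.05, 0.1 and 0.2 are rows of Table 4, 0.01 is added as a low case, and s = 0.5 is purely illustrative.

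| r | n = 5, s = 1 | n = 5, s = 0.5 | n = 17, s = 1 | n = 17, s = 0.5 | any n, s = 0 |
|---|---|---|---|---|---|
| 0.01 | 0.001 | 0.0002 | 0.012 | 0.003 | 0 |
| 0.05 | 0.023 | 0.006 | 0.208 | 0.066 | 0 |
| 0.1 | 0.081 | 0.023 | 0.518 | 0.208 | 0 |
| 0.2 | 0.263 | 0.081 | 0.882 | 0.518 | 0 |

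The column s = 0 is 4.2.4 followed literally; s = 1 is Appendix IV followed for every case.

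**The case against.** The strongest reply is that Appendix IV already settles the matter. Its wording is mandatory, Section 5.1 defines an AE broadly enough to include any symptom after dosing, and Sections 4.5 and 6.4.3 themselves call solicited reactions AEs. On this view, 4.2.4 only describes how routine diary entries are recorded, and the exclusion in 4.5 presupposes that the remaining solicited reactions are attributed. The layout of the tables in 6.4.3 does not decide whether causality is assessed.

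Much of this stands. A reader might infer that nothing in the protocol requires attribution of these reactions. The documents do not support that, because Appendix IV states a general duty. But 4.2.4 is the more specific text, has no grade exception, and agrees with 6.4.3. The reply shows that a coherent reading exists; it does not show that site staff would be bound to adopt it.

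A reader might also extend the gap to all solicited reactions. That fails for local reactions, which lie outside the diary sentence, and for reactions that meet the SAE definition, which come under the first criterion if related.

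Other safeguards exist. When the electronic diary is used, the subject's "electronic record will be available to clinicians in real time and will be the source for these data"; clinicians review the diary at least on Days 1, 2 and 7; the Safety Officer reviews data daily and the PSRT weekly (8.8); and the sponsor, PI, IRB or FDA may terminate the study at any time (9.1). These make it unlikely that a severe reaction would go unnoticed. They work by judgement, however, and do not supply the status that the second criterion requires.

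**Conclusion.** The point holds as a conflict between two instructions on an input to a pause rule. Under Appendix IV the second criterion works as intended. Under a literal reading of 4.2.4 it cannot fire on non-serious systemic diary reactions, whatever their true rate.

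The practical size is small. Between 5 and 17 infusions remained at the cut, the upper figure only if enrolment expands fully, and no event was near the trigger. With every case attributed, the trigger probability over 5 infusions is 0.001 to 0.263 for rates of 0.01 to 0.2; with none attributed it is 0. These rates are assumptions, and rates at the upper end would be high for one specific reaction at Grade 4 or prolonged Grade 3. The half-attribution columns show only how the probability responds. A reader might take the n = 17 figures as evidence that the study was materially unprotected, but the documents do not support that: the rates are assumed, and the 13 subjects observed had nothing above mild.

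The change is still worth making, because a stated safety rule should not depend on which of two sections the site follows.

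**What to change.** Add to the no-attribution sentence in 4.2.4: *except that every solicited reaction of Grade 3 or higher receives an investigator causality assessment under Appendix IV for use in the Section 4.5 pause criteria.*

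Optionally, define self-limited in 4.5 by the 3-day resolution marker that 4.2.4 already uses. That marker runs from dosing, so the sponsor should decide how to treat a reaction that begins late in the diary period. Treating such reactions as related by default would also close the gap, but it is a debatable policy choice and is not needed once causality is assessed.

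The cost is one clause and, if wanted, one definition. No visits or samples are added. The downside is a few extra causality entries and an occasional additional pause review.
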